10.1. Potential Risks

Residual risks from the risk management workbook (RMW15-0012_L) for Pipeline[™] Vantage was analyzed to determine the potential clinical harms that may be associated with the use of the Pipeline[™] Vantage device. Residual risks, as identified in the risk management work (RMW15-0012_L) are included in the below potential risks. Note that the Risk Management Workbook is a document that is continuously updated. The most current associated risks are also captured in the Instructions For Use (IFU), (P/N M993912ADOC2). Anticipated Adverse Events and Adverse Device Effects associated with use of the study device and the study procedure(s) include:

Neurological Events of Interest	An event of interest related to the target aneurysm clinical outcome and includes the following events of interest:
	Death
	Neurological Death
	Stroke*
	Major
	Minor
	ICH*
	Target Aneurysm Rupture
	Transient Ischemic Attack
	Cerebral Infarction
	Symptomatic
	Asymptomatic
	Target Aneurysm Retreatment
	Planned
	Unplanned
	Neurological Deficit (decline in mRS)*
	Focal
	Generalized
	Visual Symptoms*:
	Scintillations
	Blurred vision
	Floaters
	Diplopia
	Retinal Artery Occlusion
	Amaurosis Fugax
	Vision Loss
	Visual Field Deficit
	*Ipsilateral Territory: Presumed to be of the vascular origin of the treated vascular
	territory

Medtronic Controlled Information

PR-NV16099	Version C	Page 90 of 144	Medtronic
Procedural Events of Interest	Events representing the endovascular p treatment. Complications could be fatal Delayed. These include:		
	Access Site Complications:		
	Hematoma/hemorrhage Retroperitoneal Localized Pseudoaneurysm (PSA) Vessel occlusion Arteriovenous fistula (AVF) Deep Vein Thrombosis (DVT) Local neurogenic or nerve complica Pain Vascular Complications (Intra-Cranial o Dissection Perforation Rupture Vasospasms (vasoconstriction) Intracranial fistula formation Occlusion Thromboembolic Complications Distal Thromboembolic complii Anesthesia related complications Aspiration	r Extra Cranial):	
	Hypertension		
	Hypotension		
	Contrast Related Complications: Burning Sensation Nausea Contrast Nephropathy Visual Impairment/Visual symptom	ſS	
	Excessive Radiation Complications: Skin reddening, Blisters and ulcers,		
	Hair loss (alopecia) Cataracts		
	Late appearing cancers Systemic complications: Infection, Shoc	k, Arrhythmia	

PR-NV16099	Version C	Page 91 of 144	Medtronic

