11.1.8. Causality Assessment of Events

The relationship between the occurrence of each adverse event to the following will be assessed:

- Use of the medical device for this study, Pipeline[™] Vantage Device
- Index study procedure (on Day 0) involving initial application of the investigational medical device, and therefore not to any other procedures or treatments applied later during the clinical investigation (e.g., surgical procedures to treat SAEs).
- Use of antiplatelet therapy.

PR-NV16099	Version C	Page 100 of 144		Medtronic
------------	-----------	-----------------	--	-----------

The occurrence of each adverse event shall be assessed and categorized according to five different levels of causality for which the following definitions shall be used to assess the relationship of the adverse event to the investigational medical device, or index procedure, or use of DAPT:

1. Not Related:

Relationship to the device or procedures can be excluded when:

- the event is not a known side effect of the product category the device belongs to or of similar devices and procedures;
- the event has no temporal relationship with the use of the investigational device or the procedures;
- the serious event does not follow a known response pattern to the medical device (if the response pattern is previously known) and is biologically implausible;
- the discontinuation of medical device application or the reduction of the level of activation/exposure when clinically feasible and reintroduction of its use (or increase of the level of activation/exposure), do not impact on the serious event;
- the event involves a body-site or an organ not expected to be affected by the device or procedure;
- the event can be attributed to another cause (e.g. an underlying or concurrent illness/clinical condition, an effect of another device, drug, treatment or other risk factors);
- the event does not depend on a false result given by the investigational device used for diagnosis*, when applicable [*If an investigational device gives an incorrect diagnosis, the subject might, for example, receive an unnecessary treatment and incur all the risks that accompany that treatment, or might be incorrectly diagnosed with a serious disease. In other cases, the subject might not receive an effective treatment (thereby missing out on the benefits that treatment would confer), or might not be diagnosed with the correct disease or condition];

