- harms to the subject are not clearly due to use error;
- In order to establish the non-relatedness, not all the criteria listed above might be met at the same time, depending on the type of device/procedures and the serious event.

PR-NV16099	
------------	--

2. Unlikely:

The relationship with the use of the device seems not relevant and/or the event can be reasonably explained by another cause, but additional information may be obtained.

3. Possible:

The relationship with the use of the investigational device is weak but cannot be ruled out completely. Alternative causes are also possible (e.g., an underlying or concurrent illness/clinical condition or/and an effect of another device, drug or treatment). Cases were relatedness cannot be assessed or no information has been obtained should also be classified as possible.

4. Probable:

The relationship with the use of the investigational device seems relevant and/or the event cannot reasonably explain by another cause, but additional information may be obtained.

5. Causal relationship:

The adverse event is associated with the investigational device or with procedures beyond reasonable doubt when:

- the event is a known side effect of the product category the device belongs to or of similar devices and procedures;
- the event has a temporal relationship with investigational device use/application or procedures;
- the event involves a body-site or organ that:
 - the investigational device or procedures are applied to;
 - the investigational device or procedures have an effect on:
- the adverse event follows a known response pattern to the medical device (if the response pattern is previously known);
- the discontinuation of medical device application (or reduction of the level of activation/exposure) and reintroduction of its use (or increase of the level of activation/exposure), impact on the serious event (when clinically feasible);

ADVANCE Clinica	al Investigation Plan		
PR-NV16099	Version C	Page 102 of 144	Medtronic

- other possible causes (e.g. an underlying or concurrent illness/clinical condition or/and an effect of another device, drug or treatment) have been adequately ruled out;
- harm to the subject is due to error in use;
- the event depends on a false result given by the investigational device used for diagnosis*, when applicable;

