- In order to establish the relatedness, not all the criteria listed above might be met at the same time, depending on the type of device/procedures and the serious event.

The Investigators shall distinguish between the adverse events related to the investigational device and those related to the procedures (any procedure specific to the clinical investigation).

An adverse event can be related both to procedures and the investigational device.

Complications of procedures are considered not related if the said procedures would have been applied to the subjects in the absence of investigational device use/application.

In some particular cases the event may be not adequately assessed because information is insufficient or contradictory and/or the data cannot be verified or supplemented. The Investigators will make the maximum effort to define and categorize the event and avoid these situations. Where the Sponsor remains uncertain about classifying the adverse event, it should not exclude the relatedness and classification of the event should be noted as "possible".

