12.1. Clinical Events Committee

A CEC shall be comprised of a minimum of three (3) physicians knowledgeable in the appropriate disciplines and medical specialties pertinent to the disease state being evaluated in this clinical study and will be responsible for an independent, objective and consistent review of AEs.

Event level adjudications will be performed by a single CEC member for start and stop dates, seriousness, causality assessment, severity and outcomes for all adjudicable adverse events per CEC charter.

The CEC will independently adjudicate each subject to pre-specified Events Of Interest (EOI) which indude the primary endpoint, secondary safety endpoints, and pre-specified events of interest per **Section 10.1**.

The CEC can request additional source documentation and any potential imaging obtained in support of the adverse event to assist with adjudication.

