13.1. General Principles

A detailed statistical analysis plan (SAP) will be finalized prior to performing any analyses to expand upon the statistical methods presented below. Summary tables will summarize data for all subjects combined. All recorded data will be presented in the individual data listings sorted by site patient, and date of observation.

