13.8.3. Secondary Endpoint Analysis

All the secondary endpoints will be summarized using frequency tables presenting counts and percentages; no statistical testing will be performed against any preset thresholds for the secondary endpoints. The secondary endpoints include the following:

The following will be assessed for the effectiveness outcome measures:

- 1. Incidence of successful device implantation at the target site
- 2. Incidence of complete aneurysm occlusion (Raymond Roy Class 1) at 1- and 3-years postprocedure
- 3. Incidence of target aneurysm recurrence at 1- and 3-years post-procedure

The following will be assessed for the secondary safety endpoints:

- Incidence of major stroke in the territory supplied by the treated artery or neurological death at 2- and 3-years post-procedure
- 2. Incidence of major stroke in the territory supplied by the treated artery or neurological death at 30 days post-procedure
- Incidence of delayed intraparenchymal hemorrhage >30 days post-procedure through 1-year post-procedure

ADVANCE Clinical Investigation Plan			
PR-NV16099	Version C	Page 114 of 144	Medtronic

Incidence of subjects with disabling strokes that have a mRS decline to a score of 3 or more (mRS ≥ 3) due to a stroke-related cause assessed at a minimum of 90 days post-stroke event at 1 year, 2 year, and 3 year post-procedure

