13.8.4. Adverse Events

Adverse events will be coded according to the Medical Dictionary for Regulatory Activity (MedDRA) system dictionary.

CEC adjudicated data Tables to summarize the incidence rates will be created for each of the following groups: (At 1 year, 1- 2 years, and 2- 3 years)

- Adverse events (non-Serious) related to intervention (Procedure, anti-platelet therapy (APT)), Causal, Probable
- Serious adverse events related to Intervention (Procedure, APT)- Causal, Probable
- Adverse device effects (Non-SAE Related to Study Device- causal, probable)
- Serious adverse device effects (SAE Related to Study Device-causal, probable)
- Unanticipated serious adverse device effects (USADE)/UADE
- Adverse events by severity (Mild, Moderate and Severe) related to Device, Procedure or APT (causal, probable)

PR-NV16099

Version C

14. Ethics

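### Section 13.8.4 limits the five adverse event incidence tables that name a causality level to causal and probable, so most non-endpoint events rated only 'possible' are listed but enter no named rate

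*Combined protocol and SAP*

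**What the plan says.** Section 13.8.4 plans incidence tables from CEC-adjudicated data for six groups, at 1 year, 1 to 2 years and 2 to 3 years. The serious device-effect group reads "Serious adverse device effects (SAE Related to Study Device-causal, probable", and four other groups carry the same two levels. The sixth group, USADE/UADE, carries none.

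The causality scale is in section 11.1.8: "The occurrence of each adverse event shall be assessed and categorized according to five different levels of causality". The levels are not related, unlikely, possible, probable and causal. 'Possible' is described as a weak relationship that cannot be fully ruled out. It also receives the unresolved cases: "Cases were relatedness cannot be assessed or no information has been obtained should also be classified as possible". Where the sponsor remains uncertain, "it should not exclude the relatedness and classification of the event should be noted as" possible.

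Three other provisions bear on the point:

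- Section 13.1: "All recorded data will be presented in the individual data listings sorted by site patient, and date of observation".
- Section 12.1: a CEC member adjudicates "seriousness, causality assessment, severity and outcomes for all adjudicable adverse events per CEC charter". Separately, the CEC adjudicates each subject for the pre-specified events of interest in section 10.1.
- Section 13.8.3: secondary safety endpoints are tabulated with no causality filter. They are major territorial stroke or neurological death, delayed intraparenchymal hemorrhage, and "Incidence of subjects with disabling strokes that have a mRS decline to a score of 3 or more" (the disabling-stroke endpoint).

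**The concern.** The rating rule and the tabulation rule pull in different directions. Section 11.1.8 places doubtful cases in 'possible' so that relatedness is not excluded. Section 13.8.4 then leaves that level out of every related-event table that states a level. Section 13 names no table of all AEs or all SAEs that would pick these events up.

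The trial has one arm, so there is no concurrent rate against which to judge non-endpoint harms, and the 13.8.4 tables are the summary that section 13 names for them. Leaving 'possible' out can only keep a related-event rate equal or make it lower.

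Non-endpoint strokes are a realistic case. The SHIELD summary in section 4.2.7 reports all stroke at 6.4% (13/204) against 3.23% for the primary safety endpoint. That does not show how many events would be rated 'possible' here. It does show that strokes outside the primary endpoint occurred with an earlier device of the family.

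**Working it through.** The plan gives no figure to reproduce on this point, so the check sets the provisions side by side.

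**Step 1: the six groups in 13.8.4**, applied to an anticipated event rated 'possible' for device, procedure and antiplatelet therapy.

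| Group | Levels stated | Event counted? |
|---|---|---|
| Non-serious AEs, procedure or antiplatelet | causal, probable | no |
| Serious AEs, procedure or antiplatelet | causal, probable | no |
| Non-serious device effects | causal, probable | no |
| Serious device effects | causal, probable | no |
| USADE/UADE | none | not ordinarily, as the event is anticipated |
| AEs by severity, any of the three relations | causal, probable | no |

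Five of six groups are filtered. Three of the five causality levels fall outside them.

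**Step 2: could another named summary count it?** Take a TIA or a non-disabling minor ischemic stroke.

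- Section 13.8.3: neither is a secondary safety endpoint.
- Section 10.1: both are in the list introduced by "Anticipated Adverse Events and Adverse Device Effects associated with use of the study device and the study procedure(s) include", so the unanticipated-event table would not ordinarily take them.
- Section 12.1: both are events of interest adjudicated per subject, but section 13 names no rate table for them.
- Section 13.8.1: frequency tables are promised for outcome variables, a term that is not defined and does not name adverse events.
- Section 13.1: they appear in the listings, so they can be counted by hand, but no rate is named.

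**Step 3: the exception.** Under 11.1.6 a UADE need only be caused by or associated with the device, and no minimum level is set. An unanticipated serious event rated 'possible' can therefore enter the sixth table.

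**Step 4: events with mixed ratings.** An event probable for the procedure but only 'possible' for the device is counted under procedure and by severity, yet is missing from both device-effect tables.

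**Step 5: size per subject.** The effect on a table's rate is k/n, where k is the number of subjects whose only qualifying event is 'possible'. The target of 100 treated subjects is in section 13.2. The values of k, and a smaller denominator of 80 for a later window, are assumptions.

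- n=100: 1/100 = 1.0 point; 3/100 = 3.0 points.
- n=80: 1/80 = 1.25 points; 3/80 = 3.75 points.

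For k from 0 to 3, the shortfall is 0 to 3.0 points (n=100) or 0 to 3.75 points (n=80). A subject who also has a causal or probable event in the same table is counted anyway.

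To illustrate with assumed counts, a table showing 0/100 has a two-sided exact 95% upper limit of 3.62%. With one 'possible' subject included, 1/100 has an upper limit of 5.45%.

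**The case against.** The best case for the plan has five parts.

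1. *Some 'possible' events do reach a rate.* A reader might infer that every non-endpoint event rated 'possible' is left without one. The text does not support that, because the USADE/UADE table sets no level. The gap covers anticipated or non-serious events.

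2. *Where to cut the scale is an analysis choice.* Nothing in 11.1.8 says that 'possible' must count as related in a summary table, and 'possible' is described there as weak. So a reader should not infer a formal contradiction between 11.1.8 and 13.8.4. What stands is that the chosen cut leaves unresolved cases out and that no all-causality table makes up for it.

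3. *The tables use CEC data.* The uncertainty rule in 11.1.8 is addressed to the sponsor and investigators, and the CEC may request further source documents and imaging. It therefore cannot be assumed that every unresolved case stays at 'possible' in the adjudicated field. This weakens the mechanism but does not remove the filter.

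4. *Documents outside the review may fill the gap.* Section 13.1 announces a detailed SAP, 12.1 refers to a CEC charter, and 13.8.4 does not call its list complete. The subject-level adjudication of events of interest would be a natural basis for a further table. This is a fair limit: the point concerns what section 13 names.

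5. *No decision depends on it.* Endpoints, expedited reporting and data monitoring do not use these tables, and all events are collected and listed. That stands, and it limits the weight of the point. It also rules out any inference that events are lost or concealed.

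**Conclusion.** The point holds as a limited one about descriptive safety reporting. Five of the six table groups in 13.8.4 exclude 'possible'. An anticipated or non-serious, non-endpoint event rated no higher than that for device, procedure and antiplatelet therapy has no incidence table named in section 13. An event only 'possible' for the device is missing from the device-effect rates even when it is counted elsewhere.

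The direction is certain, since these rates can only be equal to or below rates that include 'possible'. The size is not known, because the documents give no basis for the number of affected subjects; the per-subject effect is 1 point at n=100, and the 0-to-3 range is an assumption that starts at no effect.

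A reader might infer that the primary safety result is flattered. It is not: the 7% and 14% criteria and the secondary endpoints carry no causality filter.

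Confidence is medium, because the detailed SAP and the CEC charter could already settle the matter.

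**What to change.** In 13.8.4, or in the SAP before any analysis:

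1. Add one incidence table of all AEs and all SAEs regardless of relatedness. State whether it uses site-reported or CEC-adjudicated data, since the CEC adjudicates only the events its charter makes adjudicable.
2. In the five related-event tables, show 'possible' as its own column beside causal/probable, after confirming in the CEC charter that the adjudicated field keeps that level.

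The cost is low and falls on table programming. Section 11 already collects all AEs, 11.1.8 rates each on five levels, and the CEC adjudicates causality for adjudicable events. The drawback is that related-event rates including 'possible' will look somewhat less favourable and may take in events with other causes. The separate causal/probable column lets a reader see that, and it keeps everything the plan now intends to show.

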14.1. Statement(s) of Compliance

This clinical study will be conducted in compliance with 21 CFR 812, Canada Medical Device Regulations 1998 (SOR/98-282), the latest version of the Declaration of Helsinki, laws and regional or national regulations of the countries in which the clinical study is conducted, including but not limited to local good clinical practice, data protection laws, the Clinical Investigation Agreement and the Clinical Investigation Plan.

All principles of the Declaration of Helsinki will be implemented in this clinical study by means of the informed consent process, IRB/REB approval, study training, clinical trial registration, pre-clinical testing, risk-benefit assessment, publication policy, etc.

The Sponsor will avoid improper influence on, or inducement of the subject, monitor, and Investigator(s) or other parties participating in, or contributing to, the clinical study by implementing the informed consent process, Clinical Investigation Agreements, or IRB/REB approval.

14.2. Institutional Review Boards/Research Ethics Board

The Sponsor and/or Investigator must submit this clinical protocol, subject Informed Consent Form and Investigator's Brochure to the appropriate Institutional Review Board (IRB)/Research Ethics Board (REB) and is required to forward to the Sponsor a copy of the written and dated approval.

The study (study number, clinical protocol title, and version), documents reviewed (e.g. clinical protocol, ICF, etc.) and the date of the review should be clearly stated on the written IRB/REB approval. In addition, the approval letter needs to be accompanied by an IRB/REB roster, letter of compliance, or other documentation to allow verification that the Investigator, other investigation site personnel, and/or Sponsor personnel are not members of the IRB/REB. If they are members of the IRB/REB, written documentation is required stating that he/she did not participate in the approval process.

The study will not start at a clinical site and subjects will not be enrolled until a copy of written and dated IRB/REB approval has been received by the Sponsor.

Any amendment or modification to the clinical protocol must be sent to the IRB/REB. The IRB/REB must also be informed of any event likely to affect the safety of subjects or the conduct of the study.

If the IRB/REB imposes any additional requirements (e.g. safety reports, progress reports etc.), this will be followed, if appropriate. The Sponsor will prepare the required documents and send them to the Investigator for reporting to the IRB/REB. Investigators must inform the Sponsor of any change in status of the IRB/REB approval. If any action is taken by an IRB/REB with respect to the investigation, that information will be forwarded to the Sponsor by the respective Investigator.

ADVANCE Clinical Investigation Plan Image: Clinical Investigation Plan PR-NV16099 Version C Page 116 of 144 Medtronic

The Informed Consent Form used by the Investigator for obtaining the subjects informed consent must be reviewed and approved by the Sponsor prior to submission to the appropriate IRB/REB for approval.

PR-NV16099

15. Study Administration

